7.2 General Methodology

Data analysis will be performed by Medtronic-employed statisticians or designees. A validated statistical software package will be used for the analyses of the study results (e.g., SAS).

This SAP is developed prior to data analysis and will include a comprehensive description of the statistical methods to be included in the final study report. Any change to the data analysis methods described in the CIP will require an amendment only if it changes a principal feature of the CIP. Any other change to the data analysis methods described in the CIP, and the justification for making the change, will be described in the clinical study report.

7.3 Center Pooling

The investigators of this study will conduct the study according to a common protocol and use the same CRFs to collect study data. The site study personnel will be trained prior to the study initiation at each site. Periodic study monitoring by Medtronic will ensure compliance with protocol requirements.

There is not a priori provision to exclude any sites from the analysis. The data from all sites will be pooled for analysis. To reduce the possibility of atypical results from a site overly influencing the combined results, no more than 15 subjects will be enrolled at each site, unless the site gets pre-approval from Medtronic for additional enrollments.

Due to the relatively small number of subjects expected at each center, there is no plan to use statistical methods to test for a difference among centers. Primary objective results will be summarized by center to verify there is not a site that unduly influences the results, and will be included in reports if there are concerns about the center effect.

7.4 Handling of Missing, Unused, and Spurious Data and Dropouts

Missing data are a potential source of bias when analyzing study data. A rigorous study design and execution will help prevent the incidence of missing data from occurring.

The primary analysis of the primary and secondary objectives will include subjects who maintain morphine monotherapy and provide data (per-protocol population). Sensitivity analyses will be performed for the primary and secondary objectives for VAS and NOSE using the Multiple Imputation (MI) methodology for missing data in VAS and NOSE scores for all implanted subjects. Details of the imputation method are described in Sections 7.9.2.3 and 7.9.3.3.

7.4.1 Data collected via remote visits due to COVID-19

With the onset of the COVID-19 pandemic in 2020, some study visits will be conducted remotely with the patient reported outcome data collected via telephone. Data captured via remote visit will be included in the main analyses of the primary, secondary, and additional objectives, where applicable. If more than 10% of the 6-Month Visits are completed remotely, sensitivity analyses of the Primary Objective and Secondary Objectives #1 and #2 will be conducted separately for subjects whose responses were collected exclusively during in-clinic visits and for subjects whose 6-Month data were collected remotely.

7.5 Adjustments for Multiple Comparisons

As there is only one hypothesis testing for one secondary objective, adjustment for multiple endpoints is not required.

7.6 Demographic and Other Baseline Characteristics

Demographics and baseline characteristics will be summarized in the report for enrolled subjects, implanted subjects, and per-protocol subjects who complete the 6-Month Visit.

7.7 Treatment Characteristics

The implanted pump and catheter models as well as catheter tips and locations will be summarized. The exposure to the IT therapy is defined as duration from the date of IT Therapy Initiation to the date of last study follow-up.

Subjects' pain medications will be collected and summarized. All pain medications will be coded using the appropriate version of the World Health Organization (WHO) Drug Dictionary at the appropriate Anatomical Therapeutic Chemical (ATC) level.

7.8 Interim Analyses

There is no planned interim analysis for the primary and secondary objective #1 for VAS in this study. The primary objective analysis will include all subjects in the Per-protocol Analysis Set who have completed their 6-Month Visit by the snapshot date in November 2021 (Primary Objective Analysis Set). Supporting analyses for the primary objective will include all subjects who complete the 6-Month Visit. Additional details are provided in Section 7.9.1.

7.9 Evaluation of Objectives

7.9.1 Primary Objective - Clinical Success at the 6-Month Visit

To characterize the proportion of subjects with Clinical Success at the 6-Month Visit based on changes in pain intensity using the Visual Analog Scale (VAS) and changes in opioid-related side effects using the Numerical Opioid Side Effect (NOSE) Assessment Tool.

7.9.1.1 Hypothesis

There is no formal hypothesis. The objective is to estimate the proportion of Clinical Success at the 6-Month Visit.

7.9.1.2 Experimental Design

The Clinical Success comprises 2 separate measures, pain intensity and opioid-related side effects. The measurements of pain intensity using VAS and opioid-related side effects using NOSE are described in Sections 5.2.1.1 and 5.2.1.2. Both pain intensity and opioid-related side effects are measured as a percent change from Baseline to the 6-Month Visit to calculate the Clinical Success.

Pain Intensity:

Percent change in pain intensity will be calculated as VAS at the 6-Month Visit minus VAS at Baseline, then divided by VAS at Baseline, expressed as a percentage. Individual subject percent change in pain intensity is categorized into three responder groups at the 6-Month Visit:

- Worse than Baseline: percent of change in VAS $\geq 20\%$ (increased equal to or more than 20%) if Baseline VAS is ≥ 10 , or change in VAS is ≥ 2 if Baseline VAS is < 10
- Equal to Baseline: percent of change in VAS $< 20\%$ and $> -20\%$ (increased less than 20% or decreased less than 20%) if Baseline VAS is ≥ 10 , or change in VAS is between -2 and 2 if Baseline VAS is < 10
- Better than Baseline: percent of change in VAS $\leq -20\%$ (decreased equal to or more than 20%) if Baseline VAS is ≥ 10 , or change in VAS is ≤ -2 if Baseline VAS is < 10

Opioid-Related Side Effects:

Percent change in NOSE will be calculated as NOSE at the 6-Month Visit minus NOSE at Baseline, then divided by NOSE at Baseline, expressed as a percentage. Individual subject percent change in NOSE is categorized into three responder groups at the 6-Month Visit:

- Worse than Baseline: percent of change in NOSE $\geq 20\%$ (increased equal to or more than 20%) if Baseline NOSE is ≥ 10 , or change in NOSE is ≥ 2 if Baseline NOSE is < 10
- Equal to Baseline: percent of change in NOSE $< 20\%$ and $> -20\%$ (increased less than 20% or decreased less than 20%) if Baseline NOSE is ≥ 10 , or change in NOSE is between -2 and 2 if Baseline NOSE is < 10
- Better than Baseline: percent of change in NOSE $\leq -20\%$ (decreased equal to or more than 20%) if Baseline NOSE is ≥ 10 , or change in NOSE is ≤ -2 if Baseline NOSE is < 10

Clinical Success:

A subject's Clinical Success is defined as any of the following and displayed in Figure 7-1:

1. Reduced opioid-related side effects with equal pain
2. Reduced pain with equal opioid-related side effects
3. Reduced pain and reduced opioid-related side effects

Figure 7-1 Clinical Success

Change from Baseline to the 6-Month Visit			Opioid-Related Side Effects (NOSE)		
			$\geq 20\%$ Increase	$< \pm 20\%$ Change	$\geq 20\%$ Reduction
Pain Intensity (VAS)	Worse	Equal	Better		
	$\geq 20\%$ Increase				
	$< \pm 20\%$ Change	Equal			1
	$\geq 20\%$ Reduction	Better		2	3

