9.3 Inclusion Criteria

A potential subject may be included for participation in the study if the subject has/is:

1. Willing and able to provide a signed and dated (Medtronic and Institutional Review Board (IRB) approved) Informed Consent Form (ICF) and Health Insurance Portability and Accountability Act (HIPAA) Authorization Form prior to any study procedures being performed
2. A candidate per labeling for the IDDS
3. A diagnosis of chronic, intractable, non-malignant primary back pain with or without leg pain, treatable with the IDDS
4. Current daily systemic opioid dose of >0 and ≤ 120 Morphine Milligram Equivalents (MME)
5. A Visual Analogue Scale (VAS) of ≥50 mm for pain intensity at the Baseline Visit and/or a Numerical Opioid Side Effect (NOSE) Assessment Tool ≥40 for intolerable side effects at the Baseline Visit
6. Psychological evaluation or investigator assessment of patient psychological suitability for study participation
7. Has an MRI or CT prior to enrollment verifying patent spinal canal and no clinical change in status since last imaging
8. At least 18 years old at time of enrollment
9. Willing and able to attend visits and comply with the study protocol
10. Male or non-pregnant, non-lactating female. Females must be post-menopausal or surgically sterile; or be utilizing a medically acceptable form of birth control (i.e. a hormonal contraceptive, intra-uterine device, diaphragm with spermicide, or condom with spermicide) for the duration of the study

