14.3 Primary Objective – Clinical Success at the 6-Month Visit

To characterize the proportion of subjects with Clinical Success at the 6-Month Visit based on changes in pain intensity using the Visual Analog Scale (VAS) and changes in opioid-related side effects using the Numerical Opioid Side Effect (NOSE) Assessment Tool.

Hypothesis

There is no formal hypothesis. The objective is to estimate the proportion of Clinical Success at the 6-Month Visit.

Experimental Design

The Clinical Success is comprised of 2 separate measures, pain intensity and opioid-related side effects. The measurements of pain intensity using VAS and opioid-related side effects using NOSE are described in Sections 10.17.1 and 10.17.2. Both pain intensity and opioid-related side effects are measured as a percent change from Baseline to the 6-Month Visit to calculate the Clinical Success.

Pain Intensity:

Percent change in pain intensity will be calculated as VAS at the 6-Month Visit minus VAS at Baseline, then divided by VAS at Baseline, expressed as a percentage. Individual subject percent change in pain intensity is categorized into three responder groups at the 6-Month Visit:

- Worse than Baseline: percent of change in VAS $\geq 20\%$ (increased equal or more than 20%) if Baseline VAS is ≥ 10 or change in VAS is ≥ 2 if Baseline VAS is < 10
- Equal to Baseline: percent of change in VAS $< 20\%$ and $> -20\%$ (increased less than 20% or decreased less than 20%) if Baseline VAS is ≥ 10 or change in VAS is between -2 and 2 if Baseline VAS is < 10
- Better than Baseline: percent of change in VAS $\leq -20\%$ (decreased equal or more than 20%) if Baseline VAS is ≥ 10 or change in VAS is ≤ -2 if Baseline VAS is < 10

Opioid-Related Side Effects:

Percent change in NOSE will be calculated as NOSE at the 6-Month Visit minus NOSE at Baseline, then divided by NOSE at Baseline, expressed as a percentage. Individual subject percent change in NOSE is categorized into three responder groups at the 6-Month Visit:

- Worse than Baseline: percent of change in NOSE $\geq 20\%$ (increased equal or more than 20%) if Baseline NOSE is ≥ 10 or change in NOSE is ≥ 2 if Baseline NOSE is < 10
- Equal to Baseline: percent of change in NOSE $< 20\%$ and $> -20\%$ (increased less than 20% or decreased less than 20%) if Baseline NOSE is ≥ 10 or change in NOSE is between -2 and 2 if Baseline NOSE is < 10

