5.2 Study Measures

5.2.1 Efficacy Measures

5.2.1.1 Visual Analog Scale (VAS)

Pain will be assessed using VAS. The VAS is a 100 mm line, with "No pain" on the left side of the line and "Worst pain imaginable" on the right side of the line. Subjects will be asked to mark a line perpendicular to the VAS line that best describes their average pain in the last 24 hours.

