7.9.2.1 Hypothesis

The mean change in pain intensity using VAS from Baseline to the 6-Month Visit is not worse than 0 by more than 10 points.

$$H_0: \mu \geq 0 + |M|$$

$$H_A: \mu < 0 + |M|$$

Where μ is the mean change in VAS from Baseline to the 6-Month Visit and $|M|$ is the absolute value of non-inferiority margin of 10.

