7.9.2.3 Analysis Methods

The change in VAS as well as VAS at both Baseline and the 6-Month Visit will be summarized using descriptive statistics, (e.g., mean, standard deviations, etc.). The non-inferiority null hypothesis will be tested using a one-sided 0.025 alpha level one sample t-test. The upper bound of the 95% CI of the mean change must be less than 10. If non-inferiority is met, a two-sided 0.05 alpha level t-test for superiority (vs. 0 change from Baseline) will be performed. If the distribution of the change in VAS doesn't meet normality assumption (Shapiro-Wilk test), an appropriate non-parametric analysis such as Wilcoxon signed rank test will be performed. The primary analysis will use all the implanted subjects who maintain morphine monotherapy and provide data at both Baseline and 6-Month Visits.

Two sensitivity analyses will be performed, one will include subjects who provide data (completers) and one will include all implanted subjects. The sensitivity analysis of all implanted subjects will be performed using MI method for missing data at the Baseline and the 6-Month Visits. For missing VAS at

the scheduled 6-Month Visit, if an Unscheduled Visit occurred within the 6-Month Visit window, and the VAS is collected at the Unscheduled Visit, the VAS from the Unscheduled Visit will be used in the analysis of the 6-Month Visit. Otherwise, the missing VAS will be imputed using MI. Prior to the use of MI, the distributions of the continuous variables will be assessed for normality and the need for transformation if they are not normally distributed. The model variables in MI may include the following when deemed appropriate: study site, subject age, gender, primary diagnosis, VAS at Baseline, 1-Month Visit, 3-Month Visit. The fully conditional specification (FCS) method with 10 burn-in iterations within SAS and 10 repetitions ($M = 10$) will be used for imputation. Constraints will be set so that the imputed VAS are restricted to values ranging from 0-100. If the MI procedure is unable to successfully impute values within that range, the constraints will be applied after imputation, such that any values less than 0 will be set to 0, and any values greater than 100 will be set to 100. Following imputation, the objective will be evaluated using MI analysis method in SAS.

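### Above a Baseline VAS of 83.3 mm pain cannot be classed as worse, some rises of 11 to 16 mm can count within Clinical Success, and no planned sensitivity analysis tests the classification

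*SAP*

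**What the plan says.** SAP 5.2.1.1 fixes the range of the pain measure: "The VAS is a 100 mm line", ending at the worst pain imaginable.

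SAP 7.9.1.2 sorts each subject by percent change in VAS from Baseline to 6 months. *Worse* applies when the VAS has "increased equal to or more than 20%) if Baseline VAS is" 10 or more. *Equal* applies when it has "increased less than 20% or decreased less than 20%) if Baseline VAS is" 10 or more. *Better* is a fall of at least 20%. Below a Baseline of 10 the percent rule gives way to an absolute change of 2 points. Protocol 14.3 has the same definition ("increased equal or more than 20%) if Baseline VAS is" 10 or more). Neither document has a rule for the top of the scale.

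*Equal* pain enters Clinical Success through one cell only: "Reduced opioid-related side effects with equal pain". The other two success cells need pain to fall by at least 20%.

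Protocol 9.3 admits subjects with "A Visual Analogue Scale (VAS) of ≥50 mm for pain intensity at the Baseline Visit" and/or a NOSE of at least 40, with no upper limit on VAS.

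SAP 7.9.1.3 plans three sensitivity analyses of Clinical Success, plus a conditional one for remote visits. They vary the subjects included, the handling of missing data or the mode of collection. None varies the classification.

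**The concern.** A percent-change rule on a bounded scale loses room at the top. Entry on a VAS of 50 mm or more puts subjects in the upper half of the scale, where this matters. The plan already accepts that percent change misbehaves at one end, since it switches to an absolute rule below 10. Only subjects who enter on NOSE can be down there, while the end nearer the VAS entrants is left open.

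Protocol 6.2 says the composite was chosen because a more invasive therapy has to be justified by an overall benefit. The *Equal* pain cell carries the part of that argument in which side effects fall and pain control is held. If *Equal* can include a clear rise in pain, the reported success rate may contain subjects for whom pain control was not held, and nothing planned would show how many.

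**Working it through.** **The plan's own figures.** The only calculation that uses the 10-point margin is the power for Secondary Objective #1 (SAP section 6: n = 50, one-sided alpha 0.025, margin 10, true difference 0, SD 19 on the 0-100 scale). Noncentrality = (10/19) × √50 = 3.72 with 49 df gives 95.4% power; the plan states 95%. The exact interval for 35/50 is 55.4% to 82.1%, as stated in SAP 7.9.1.3. Neither figure is in dispute.

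**Where *Worse* becomes impossible.** *Worse* needs 1.2 × B ≤ 100, where B is Baseline VAS, so B ≤ 83.3 mm.
- B = 83: the largest possible rise is 17 mm, and 17/83 = 20.5%. *Worse* is just reachable.
- B = 84: the largest possible rise is 16 mm, and 16/84 = 19.0%. *Worse* is unreachable here and at every higher Baseline.

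**Which rises are *Equal*.** A rise r is *Equal* when r/B < 0.20 and B + r ≤ 100. For whole-mm values:

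| Rise (mm) | Baselines at which it is *Equal* |
|---|---|
| 10 | 51-90 |
| 11 | 56-89 |
| 12 | 61-88 |
| 13 | 66-87 |
| 14 | 71-86 |
| 15 | 76-85 |
| 16 | 81-84 |
| 17 or more | none |

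At lower Baselines the same rises are *Worse*: 10 mm at B ≤ 50, 16 mm at B ≤ 80.

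**Worked case.** VAS 84 to 100 is +19.0%, hence *Equal*, although the subject ends at the worst pain imaginable. NOSE 9 to 7 is a change of −2 from a Baseline below 10, hence *Better*. The subject was eligible on VAS and is a Clinical Success.

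**How many subjects.** The documents give no Baseline VAS distribution, so this is an illustration. Assumptions: Baseline normal (mean 72, SD 13) truncated to 50-100; change normal with the plan's SD of 19 mm; 6-month values clipped to 0-100.

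| Mean change (mm) | *Equal* with rise ≥10 mm | of which Baseline above 83.3 mm |
|---|---|---|
| 0 | 8.7% | about 3.4% |
| −10 | 5.0% | 1.7% |
| −20 | 2.2% | 0.7% |

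About 19% of subjects have a Baseline above 83.3 mm under these assumptions. With Baseline means of 60 to 80 and SDs of 10 to 15, the share above 83 mm runs from about 1% to 36%. The share *Equal* with a rise strictly above 10 mm then runs from 3.6% to 10.3% at zero mean change and from 1.0% to 2.4% at −20 mm.

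All these shares are before the NOSE condition. With 50 evaluable subjects, 8.7% is 0.087 × 50 = 4.4 subjects and 2.2% is 1.1 subjects. Only those who also have a NOSE reduction count as successes, and each one moves the primary estimate by 1/50 = 2 points.

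**The case against.** **The 10-point margin.** A reader might infer that the primary endpoint contradicts the plan's own margin by accepting individual rises of more than 10 mm. The documents do not support that. In SAP 7.9.2.1 the mean change is what is bounded (|M| "is the absolute value of non-inferiority margin of 10"), and SAP 7.9.2.3 tests a group quantity: "The upper bound of the 95% CI of the mean change must be less than 10". With an SD of 19 mm, many individuals rise by more than 10 mm even when the mean change is zero. No passage sets a 10-mm limit for one subject. Comparing the two says something about stringency; it does not show an inconsistency.

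**Loss of pain control goes unseen.** A reader might also infer that the plan cannot detect worsening in subjects with the most severe pain. That is true of the *Worse* category above 83.3 mm but not of the plan. Secondary Objective #1 reports and tests mean VAS change and summarizes percent change, and a move from 84 to 100 counts there in full. It does not show which of those subjects were counted as Clinical Successes.

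**The rule always flatters the result.** This holds only against a rule that adds a mm criterion to the 20% rule. Against a plain 10-mm rule, the 20% rule is the stricter one below 50 mm: a rise of 6 mm from a Baseline of 30 is *Worse*, and such a subject can enter on NOSE.

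**A documented choice.** Protocol 6.2 cites an earlier randomized trial in malignant pain as precedent, and the objective is descriptive with no hypothesis. Both points are fair. As cited, though, the precedent gives a 20% reduction and equal pain scores; it does not say that equal pain extends to a 20% increase.

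**Redefining the endpoint.** All 93 subjects are enrolled. The definition also stands in protocol 5.1.1 and 14.3, and under protocol 14.1 a change to a principal feature needs an amendment. An added mm criterion has its own asymmetry: at a Baseline of 84, *Worse* would need +10 mm and *Better* −16.8 mm. On the assumptions above with zero mean change, it raises *Worse* from 19% to 28% of subjects. This objection stands against replacing the primary definition. It does not stand against a sensitivity analysis.

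**Conclusion.** The point holds as a gap in the primary endpoint's classification. Three parts are exact and need no assumption: *Worse* pain is empty by construction above a Baseline of 83.3 mm; some rises of 11 to 16 mm are *Equal* for whole-mm Baselines within 56 to 89; and such subjects are Clinical Successes if NOSE is also reduced. That there is no high-end guard and no sensitivity analysis on the classification follows from reading both documents.

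The size is unknown. The illustration of about 9%, 5% and 2% of subjects rests on an assumed Baseline distribution, a change SD of 19 mm and mean changes of 0, −10 and −20 mm. It is an upper limit on the effect under those assumptions, because the NOSE condition removes some of these subjects. Set beside a planned interval 26.7 points wide, the likely effect is modest. Whether any such subject exists can be settled only from the data.

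**What to change.** Keep the 20% rule as the primary definition, so that the SAP and protocol still agree. In SAP 7.9.1.3 add:

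1. One sensitivity analysis of Clinical Success in which pain is *Worse* if VAS rises by at least 20% or by at least 10 mm, and *Equal* if it is neither *Better* nor *Worse*. State that 10 mm is a chosen individual cut-off and not an application of the non-inferiority margin.
2. The number of Clinical Successes whose VAS rose by 10 mm or more.
3. The number of subjects with a Baseline VAS above 83 mm.

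The cost is one extra classification and two counts on data already collected, with no change to study conduct. The success rate in the sensitivity analysis may be slightly lower than the primary one. If few subjects are affected, the report gains a statement of robustness; if several are, readers of the success rate need to know.

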7.9.1.3 Analysis Methods

The proportion of subjects with Clinical Success and its exact binomial two-sided 95% confidence interval will be reported. The primary analysis method will use all the implanted subjects who maintain morphine monotherapy and provide data at both Baseline and the 6-Month Visits through the snapshot date in November 2021 (Primary Objective Analysis Set). Assuming the estimated proportion of Clinical

Success is 70%, with a sample size of 50 subjects, the exact two-sided 95% confidence interval (CI) would be 55.4-82.1%, with a confidence width of 26.7%. The widest 95% CI would be at 28.9% for an estimated proportion of Clinical Success of 50% (95% CI 35.5-64.5%).

Three sensitivity analyses will be performed: (1) the proportion of subjects with Clinical Success and its 95% CI will be reported in subjects who maintain morphine monotherapy and provide data at the Baseline and the 6-Month Visits (Per-protocol Analysis Set), (2) the proportion of subjects with Clinical Success and its 95% CI will be reported in subjects who provide data at the Baseline and the 6-Month Visits (completers), (3) the proportion of subject with Clinical Success and its 95% CI will be reported in all implanted subjects with imputation method of MI for those who have missing VAS or NOSE at the Baseline or the 6-Month Visit. Details of the imputation method are described in Sections 7.9.2.3 and 7.9.3.3.

If more than 10% of the 6-Month Visits within the Per-protocol Analysis Set are conducted remotely, an additional sensitivity analysis of the Per-protocol Analysis Set will be performed as described in Section 7.4.1.

